7 ASSESSMENTS

7.1 Screening/Baseline Assessment

Prior to enrollment, each participant will undergo a medical screen, be introduced to study procedures,

The SATURN Study [CONFIDENTIAL – DO NOT REDISTRIBUTE]

and undergo informed consent. Screening will be conducted within 30 days of baseline assessment. If any of the screening labs were performed as part of standard of care within 4 weeks of the screening, these labs will be used for screening.

If the patient qualifies and consents to participate, they will undergo baseline assessments. Baseline labs that were done within the previous 4 weeks will be accepted as baseline labs; if there are no labs for >4 weeks, these will be repeated. If any of the following baseline procedures were performed and documented in the medical chart at part of standard of care within 2 months of the baseline visit, these will be accepted as the baseline assessment: RHC, PFTs, 6MWDT, 12-Lead ECG.

All participants will start taking the study drug on the morning of Day 1, the day after the baseline assessment. All participants will follow up in person for assessments at Weeks 4, 12, and 24. Participants will also be contacted electronically and/or by telephone on Weeks 2, 8, 16, 20, 28. Participants will continue the study drug for 24 weeks with the final in person assessment at Week 24. A final follow-up electronically or by telephone will be performed at week 28 (4 weeks after treatment completion). If participants do not complete the 24 weeks of treatment for any reason, every effort will be made to conduct the Week 24 final assessment at the time of treatment termination and the participant will be followed until at least 4 weeks after stopping the study drug (longer if necessary to follow AEs). If the participants are enrolled in the open-label extension, they will be contacted by telephone on Weeks 26 and 36. A final in-person assessment will occur at Week 48.

Biological samples:

- Blood:
 - 6 ml blood for serum concentration of H01 and metabolites
 - 6 ml blood for serum HA level and biomarkers
 - 6 ml blood for CBC
 - 6 ml blood for CMP
- Urine:
 - Pregnancy test for females of child-bearing potential (serum pregnancy test may be substituted for urine)
- Exhaled breath condensate:
 - Concentration of HA levels, H01 and metabolites

7.2 Laboratories for Central Study-specific Testing

Lab testing will be done at the trial site laboratory used in the provision of standard of care services will process routine bloodwork (as above). The laboratory manual and study operations manual will specify procedures for when tests in the study protocol are not completed as standard of care. The manual will also detail which tests may need to be processed for shipping to alternative laboratories at Stanford, two of which are referenced below.

7.3 Clinical Improvement

Clinical improvement in this study will utilize the RHC, 6MWD test, PFTs, and patient symptom score reports.

RHC at rest and with exercise will be performed in accordance with standard procedures by a trained pulmonologist in a cardiac catheterization laboratory and standard sedation medications may be used. This procedure typically takes less than one hour.

6MWD test and PFTs will be performed in the clinic at specified visits in accordance with standard guidelines and will be carried out by trained study staff.

Quality of life questionnaires will be performed at selected time points and will include questions to measure physical activity, respiratory symptoms, pain, general health, mental and emotional wellbeing.

8 STUDY DRUG PROCEDURES

8.1 Treatment Assignment

Up to 16 eligible participants will be randomly assigned to H01 or placebo in a 5:3 ratio using a computer-generated randomization scheme, stratified by PH type, developed by an unblinded biostatistician at Stanford University. The code used to generate the allocation, along with the seed used in the random number generation, will be stored on secure servers and maintained by the unblinded biostatistician.

8.2 Blinding

This is a double-blind study design. Participants, study investigators, and clinicians will be blinded. All doses of study drugs and placebo will be prepackaged by a central study pharmacy. The central pharmacy will coordinate randomization with the independent biostatistician for randomization codes. The allocation codes and labeled product will be used by dedicated study personnel who will administer

product to enrolled and randomized participants. An SOP will govern the blinding process. Any break in the blinding process will be reported to the DSMC and principal investigator.

8.3 Formulation of Test and Placebo Medications

H01 will be supplied by a manufacturer in Europe that holds current good manufacturing practice (GMP) certification. Specifically, the tablet formulation approved in the European Union called Isochol 400 mg will be used and provided by the marketing authorization holder, Zentiva. [name].

Under normal conditions, unopened H01 has a reported shelf-life by the manufacturer of 3 years. The drug product will be stored at a temperature under 25 °C in bottles, and bottles will be tightly closed in order to protect from moisture, in accordance with the storage instructions on the Iscohol 400mg label.

The placebo tablets used in this trial are selected to match the general shape, size and color of H01 but are not identical. Storage and dispensing of medications H01 and placebo product will be performed at controlled room temperature, 59° to 77°F (15° to 25°C) and protected from light and moisture by study-designated pharmacy personnel. Study drug will be dispensed to enrolled participants based on site-level standard operating procedures. Study drug will remain in the original bottles until the time of release of the product to patients for home administration. A site Drug Accountability Log will be maintained by site personnel. This log is subject to audit and will be signed off by the site investigator at the end of the trial. A temperature log will be utilized by the IDS to ensure compliance with temperature requirements.

8.4 Possible Reasons for Discontinuation of Treatment

All reasons for discontinuation from study drug will be captured in study CRFs enabling for the ability to differentiate treatment discontinuation from study withdrawal. These include the following reasons:

- Completed 24 weeks of treatment of the blinded study or 48 week of the open-label extension
- Grade ≥ 3 Adverse Drug Reactions
- Withdrawal of consent
- Physician request

Investigators and study staff are reminded of the importance of participant retention in the case of treatment discontinuation and should take steps to prevent missing data that will be critical to the interpretation of the study results. Investigators and study staff should remind participants of the importance of continued participation in laboratory and clinical monitoring. Participants who discontinue study drug should continue follow-up when possible. This concept will be reinforced in the Informed Consent Form (ICF).

In the case of missing data for participant disposition for a randomized participant, a vital records search will be undertaken.

9 MONITORING AND REPORTING OF ADVERSE EVENTS

9.1 Adverse Events Definition

An adverse event (AE) is any untoward or unfavorable medical occurrence in humans which occurs during the participant's participation of a clinical study, whether or not considered drug related. Any change in clinical status, routine labs, physical examinations, etc. that is considered clinically significant by the study investigator are considered AEs.

9.2 Suspected Adverse Reaction Definition

A Suspected Adverse Reaction is any adverse event for which there is a reasonable possibility that the investigational drug caused the AE. For the purposes of safety reporting, 'reasonable possibility' means there is evidence to suggest a causal relationship between the drug and the adverse event. A suspected adverse reaction implies a lesser degree of certainty about causality than adverse reaction, which means any adverse event caused by a drug.

9.3 Serious Adverse Event or Serious Adverse Reaction Definition

An AE or suspected adverse reaction or adverse reaction is considered serious if, in the view of either the PI or sponsor, it results in any of the following outcomes:

- Death
- Life-threatening AE: it is considered "life-threatening" if its occurrence, in the opinion of the investigator or sponsor, places the participant at immediate risk of death from the reaction as it occurred. It does not include an AE or SAR that, had it occurred in a more severe form, might have caused death.
- Persistent or significant incapacity or substantial disruption of the ability to conduct normal life functions
- Inpatient hospitalization or prolongation of existing hospitalization
- Congenital abnormality or birth defect
- Necessary surgery or medical device intervention to prevent fatal or permanent adverse effects
- Important medical event that may not result in one of the above outcomes, but may jeopardize the health of the study participant or require medical or surgical intervention to prevent one of the outcomes listed in the above definition of serious adverse event

9.4 Unexpected Adverse Event or Reaction Definition

An adverse event or suspected adverse reaction is considered "unexpected" if it is not listed in the

The SATURN Study [CONFIDENTIAL – DO NOT REDISTRIBUTE]

Investigator Brochure or package insert or is not listed at the specificity, severity or rate of occurrence that has been observed. The below summary includes adverse reactions from product labels for H01 in Europe.

- Cantabiline® 400 mg (France)

Undesirable effects: Occasional cases of diarrhea and isolated reports of allergic skin reactions.

- Cantabilin® 300 mg (Italy)

Undesirable effects: Diarrhea, anaphylactic reactions, including urticaria, itching, dyspnea, Quincke's edema and hypotension that can evolve to anaphylactic shock.

- Cholspasmin® forte 400 mg (Germany)

Undesirable effects: With prolonged administration of higher doses, soft stool or diarrhea may occur; fullness, constipation and stomach pressures are also reported (<0.01%) hypersensitivity reactions may occur, which can manifest as skin changes (< 0.01%).

- Isochol® 400 mg (Czech Republic)

Undesirable effects: Rare frequency of headache and rash (<0.001)

9.5 New Fact

A new fact is defined as any new data that may lead to a reassessment of the risk-to-benefit ratio of the research or of the product being researched, changes in the use of this product, in the conduct of the research, or to the documents relating to the research, or data that may lead to the suspension, discontinuation or modification of the research protocol or similar research.

9.6 Identification of Adverse Events

As all participants in this study will have pre-existing medical conditions, those pre-existing conditions will not be considered adverse events. New events that occur or worsening (through frequency or intensity) of pre-existing conditions will be considered as adverse events.

Adverse events (including SAEs) may be discovered through any of these methods:

1. Observing or interviewing the participant.
2. Procedures / laboratories as performed as part of participating in the study.
3. Receiving an unsolicited complaint from the participant.

The investigator will provide the following information about an AE:

- Date of onset and resolution
- Severity, graded using the NIH Common Terminology Criteria for Adverse Events (CTCAE), Version 5.0
- Action taken with study drug product
- Changes in study drug dosing
- Causal relationship to study drug

- Outcome

All reportable drug adverse events as defined above will be recorded on the appropriate AE/SAE CRF form starting after consent has been obtained until Day 196 (ie at least 30 days after the last dose of study drug).

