9	MONITORING AND REPORTING OF ADVERSE EVENTS	25
9.1	Adverse Events Definition.....	25
9.2	Suspected Adverse Reaction Definition	25
9.3	Serious Adverse Event or Serious Adverse Reaction Definition.....	25
9.4	Unexpected Adverse Event or Reaction Definition.....	25
9.5	New Fact	26
9.6	Identification of Adverse Events	26
9.7	Follow-up of Adverse Events	27
9.8	Guidelines for Assessing Severity of an Adverse Event.....	27
9.9	Guidelines for Determining Causality	27
9.10	Serious Adverse Events	28
9.11	Unexpected Non-serious Adverse Events.....	28
9.12	Reporting to Health Authority	28
9.12.1	Standard Reporting (IND Annual Report).....	28
9.12.2	Expedited Reporting	28
9.13	Protocol Violations	29
9.14	Reasons for Early Termination	29
9.14.1	Halting the Study	29
9.15	Data Safety Monitoring.....	30
10	STATISTICAL METHODS AND CONSIDERATIONS.....	30
10.1	Analysis Population	30

The SATURN Study [CONFIDENTIAL – DO NOT REDISTRIBUTE]

10.2	Descriptive Statistics.....	30
10.3	Analysis of Primary Endpoints	31
10.4	Analysis of Secondary Endpoints	31
10.5	Analysis of Exploratory Endpoints	31
10.6	Missing Data Handling	32
10.7	Sample Size and Randomization	32
11	DATA COLLECTION, RETENTION AND MONITORING	32
11.1	Data Collection Instruments	32
11.2	Data Management Procedures	33
11.3	Data Quality Control and Reporting.....	33
11.4	Archival of Data.....	33
11.5	Availability and Retention of Investigational Records	34
11.6	Subject Confidentiality	34
12	ETHICAL CONSIDERATIONS	34
12.1	IRB and HIPAA.....	34
12.2	Potential Participant Risks	36
12.3	Potential Benefits	36
13	Abbreviations	36
14	References.....	37

1 **BACKGROUND**

1.1 **Introduction**

This is a prospective, randomized, double-blind, study of H01 of 24 weeks in adults with pulmonary hypertension (PH) with an optional open-label extension (extension to 48 weeks). The primary objective of this double-blinded study is to evaluate the clinical efficacy of H01 over 24 weeks. Secondary objectives are to investigate the safety and tolerability of H01 and pharmacokinetic (PK) and pharmacodynamic (PD) markers in this population. Following IRB approval and written informed consent, a total of 16 participants will be enrolled, randomized approximately 2:1 (H01 1600 mg/day : placebo), stratified by PH type, and treated for 24 weeks. Data from this study will inform future larger studies. Participants will have the opportunity to extend their participation an additional 24 weeks by consenting to an open-label extension.

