Exploratory Endpoints	
 Change in inflammatory markers (ESR, HSCRP) Change in pro-inflammatory cytokines Change in Forced Expiratory Volume in one second (FEV1) Change in Forced Vital Capacity (FVC) from pulmonary function test (PFT) Change in Total Lung Capacity (TLC) from pulmonary function test (PFT) Change in Lung diffusion capacity (DLCO) from pulmonary function test (PFT) Change in exhaled breath condensate (EBC) hyaluronan concentrations over the study period Describe the pharmacokinetics (H01 and metabolite serum concentrations) Describe HA fragment size

The SATURN Study [CONFIDENTIAL – DO NOT REDISTRIBUTE]

Planned sample size	16
Number of Sites	1
Duration of Participation	
Total study period of the blinded study: 28 weeks
 
Total study period including open-label extension: 48 weeks
 
 ▪ Screening Period: up to 4 weeks ▪ Treatment Period of the blinded study: 24 weeks ▪ Treatment Period including open-label extension: 48 weeks ▪ Follow-up Period: 4 weeks after treatment period ends (Week 24) if not enrolled in the open-label extension
Dose Schedule	
 ▪ Participants randomized to treatment will receive two H01 400 mg tablets BID (1600 mg/day) for 24 weeks or through Week 48 if enrolled in the open-label extension ▪ Participants randomized to placebo will receive two placebo tablets BID for 24 weeks

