6 SCHEDULE OF ASSESSMENTS

Schedule of Assessments for SATURN Trial

Visits	Screen		Active							FU			
	Screening	Baseline	Week 2	Week 4	Week 8	Week 12	Week 16	Week 20	Week 24	Week 26**	Week 28+	Week 36**	Week 48 **
Day ^a	0	1	14±3	28±3	56 ± 3	84±7	140 ± 7	168±7	196±7	210±3	224±3	280±7	364±7
Telephone or Email Contact			x		x		x	x		x**	x^	x**	
Informed Consent	x												
History and physical													
Medical history	x	x											
Symptom assessment/NYHA	x	x	x	x	x	x	x	x	x	x**	x+	x**	x**
Medications	x	x	x	x	x	x	x	x	x	x**	x+	x**	x**
Vital Signs & Weight	x		x		x			x			x**		x**
Physical Examination	x		x		x			x			x**		x**
EMPHASIS-10 / SGQ	x		x		x			x			x**		x**
General Testing													
Comprehensive Metabolic Panel	x		x		x			x		x	x**		x**
CBC	x		x		x			x		x	x**		x**
Pregnancy test (If Indicated) ^a	x		x	x*	x	x*	x*	x*	x	x**	x**	x**	x**
12-Lead ECG	x												
Endpoint assessment													
Right Heart Catheterization	x								x				
Serum & EBC hyaluronan	x		x		x			x		x	x**		x**
6 minute walk distance	x		x		x			x		x	x**		x**
NT-pro-BNP	x		x		x			x		x	x**		x**
PFT with ABG	x							x		x			
Inflammatory markers	x		x		x			x		x	x**		x**
Serum and EBC drug levels	x		x		x			x		x	x**		x**
Study Procedures													
Medication Pill Count			x	x	x	x	x	x	x	x**	x**	x**	x**
Adverse Events	x	x	x	x	x	x	x	x	x	x**	x+	x**	x**
Study Termination										x^			x**

*Home pregnancy test permitted

^ Only for subjects not participating in OLE (Open-Label Extension)

**Only for subjects participating in OLE (Open-Label Extension)

+ For participants in OLE (Open-Label Extension) and those not participating in OLE

a. Pregnancy tests need to be done monthly in OLE (Open-Label Extension). Participants will be given home pregnancy test kits to take home.

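### Section 9.6 ends AE/SAE form recording at a fixed Day 196, which is not 30 days after the last dose at Week 24 or Week 48 and conflicts with later scheduled AE assessments

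*Combined protocol and SAP*

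**What the plan says.** Section 9.6 has AE and SAE forms completed "starting after consent has been obtained until Day 196 (ie at least 30 days after the last dose of study drug". It gives no separate limit for the open-label extension.

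Sections 1.2, 2.1 and 3.1 have extension participants on drug until Week 48. In the Section 6 schedule the AE row is marked at every visit, including Weeks 26, 36 and 48 under the footnote "Only for subjects participating in OLE (Open-Label Extension" and Week 28 under the footnote "For participants in OLE (Open-Label Extension) and those not participating in OLE".

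Follow-up length is worded in two ways. Section 1.2 has "Follow-up Period: 4 weeks after treatment period ends (Week 24) if not enrolled in the open-label extension", and Section 7.1 also says 4 weeks. Section 3.1 says 30 days. For the extension, Section 1.2 lists "Treatment Period including open-label extension: 48 weeks" and "Total study period including open-label extension: 48 weeks". Section 7.1 makes Week 48 the final in-person assessment, and the schedule has no later column.

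Section 10.4 summarises AEs and SAEs by type and arm over the ITT denominator and names no period. In Section 4.2 the safety endpoint has no time frame, while the other five secondary endpoints each have one.

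**The concern.** A fixed study day cannot serve as a rule tied to the last dose when the last dose may fall at Week 24 or Week 48. Site staff who follow Section 9.6 and staff who follow the schedule would stop completing the AE form on different dates.

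Safety and tolerability is the first secondary endpoint, and Section 2.6 extends the safety hypothesis to the additional 24 weeks. Section 2.1 gives 6 months (n=29) as the longest reported administration. For participants first randomised to H01, most of the extension goes beyond that. SAEs have their own reporting route in Section 9.10, but expected, non-serious events such as labelled diarrhea depend mainly on the Section 9.6 form.

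**Working it through.** **Inputs.** End of recording: Day 196 (Section 9.6). First dose: morning of Day 1 (Section 7.1). Last dose: Week 24, or Week 48 in the extension (Sections 1.2, 2.1, 3.1). Day labels: Section 6. The last dose is taken to fall at the nominal end of treatment.

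**Two clocks.** The calendar clock is week × 7. The label clock is the day printed in the schedule. They agree up to Week 12 and differ by 28 days from Week 16 on.

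| Visit | Calendar day | Day label | Label − calendar | Later than Day 196? |
|---|---|---|---|---|
| Week 12 | 84 | 84 | 0 | no |
| Week 16 | 112 | 140 | 28 | no |
| Week 20 | 140 | 168 | 28 | no |
| Week 24 | 168 | 196 | 28 | no |
| Week 26 | 182 | 210 | 28 | by label only |
| Week 28 | 196 | 224 | 28 | by label only |
| Week 36 | 252 | 280 | 28 | on both |
| Week 48 | 336 | 364 | 28 | on both |

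**The plan's own figure, at least 30 days after the last dose.** Days covered = 196 − day of last dose.

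- Last dose at Week 24, calendar: 196 − 168 = 28.
- Last dose at Week 24, label: 196 − 196 = 0.
- Last dose at Week 48, calendar: 196 − 336 = −140.
- Last dose at Week 48, label: 196 − 364 = −168.

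The figure is not reproduced on either clock. To have 30 days by Day 196, the last dose would have to fall on or before Day 196 − 30 = 166.

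**Where a 30-day rule would end.** At Week 24: 168 + 30 = Day 198 by calendar, or 196 + 30 = Day 226 by label. At Week 48: 336 + 30 = Day 366, or 364 + 30 = Day 394.

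**Conflict with the schedule.** Two AE assessments (Weeks 36 and 48) fall after Day 196 by calendar. Four (Weeks 26, 28, 36 and 48) do so by label.

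**Contact after the last open-label dose.** Section 1.2 gives 48 weeks in total and 48 weeks of treatment: 48 − 48 = 0 weeks of follow-up. The schedule agrees, since its last column is Week 48 and study termination is marked there.

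**The case against.** The strongest reply is that the sentence carries its own correct rule. At least 30 days after the last dose would take recording past Week 48 for an extension participant. Day 196 is calendar Week 28, so it looks like the end of blinded follow-up, not updated when the extension was added. That origin is an inference. Other text also points to continued capture. Section 9.1 defines AEs over the whole of participation, Section 9.10 sets no end date for SAE reporting, and Sections 9.7 and 9.14 follow certain events until they resolve or stabilise. This stands, and it limits the point to a conflict over which text governs. It does not remove the point, because the protocol does not say whether the day or the gloss prevails.

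A reader might infer that AE data will be lost for the 140 of 168 extension days that lie after Day 196. The documents do not support that: the number describes the literal cut-off, and the schedule contradicts the cut-off.

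A reader might also infer that open-label H01 events in former placebo participants will be counted in the placebo arm. That needs several steps. The schedule must govern. Former placebo participants must take H01, which Sections 1.1 and 2.1 imply while Section 1.2 says only "Participants randomized to placebo will receive two placebo tablets BID for 24 weeks". The analyst must also pool the two periods. Section 10.1 analyses by assigned arm, but Section 10.4 is silent on period, and silence does not set a default. The between-arm test is optional, onset dates are collected, and Section 11.2 lists a statistical analysis plan in the trial master file that could define the period. No size can be put on this, because the documents give neither extension uptake nor an AE rate.

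The gap between 28 and 30 days is small in itself. It matters only because the same sentence has to be rewritten anyway.

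**Conclusion.** The point holds as an error in a stated rule. Day 196 is not at least 30 days after a last dose at Week 24 (28 days by calendar, 0 by label), and it precedes the last extension dose by 140 days by calendar or 168 by label. It contradicts the AE assessments scheduled for extension participants at Weeks 36 and 48, and on the schedule's labels also those at Weeks 26 and 28. The figures assume dosing to the nominal end of Week 24 or Week 48; no other assumption is needed.

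What is shown is an internal conflict that most likely dates from the addition of the extension. A decision to stop collecting AEs is not shown, and neither is a loss of data. The missing contact after the last open-label dose is a real but modest gap. The missing AE period in Section 10.4 is a secondary clarification.

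**What to change.** 1. In Section 9.6, replace the fixed day with 30 days after each participant's own last dose of blinded or open-label study drug. For someone who stops early, this would end recording sooner than Day 196. If the longer window is wanted for them, say so explicitly.
2. In Section 6, reduce each day label from Week 16 on by 28.
3. Align the follow-up length in Sections 1.2, 3.1 and 7.1 with Section 9.6. Thirty days is already the figure in Sections 3.1 and 9.6.
4. Add one closing telephone contact about 30 days after the last open-label dose, which is calendar Day 366 for a participant who stops at Week 48.
5. In Section 10.4, state that the by-arm AE and SAE summary covers events with onset before the first open-label dose, or through follow-up for those not in the extension. Tabulate open-label events separately by original arm.

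The cost is wording changes, one call per extension participant and one more table. Onset dates are already collected, so the split by period needs no new data. The call takes participation slightly past the stated 48 weeks, so the protocol and consent form must be amended and approved by the IRB (Section 12.1).
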